2.4.5.3 Deaths

The following summaries of deaths will be generated.

- Number (%) of patients who died by study period (on-study, on-treatment, post-study)
- Deaths in nonrandomized patients or randomized but not treated patients
- Treatment-emergent adverse events leading to death (death as an outcome on the adverse event case report form page as reported by the Investigator) by primary SOC , HLG, HLT, and PT showing number (%) of patients sorted by internationally agreed SOC order, with HLG, HLT, and PT presented in alphabetical order within each SOC.

2.4.5.4 Analyses of laboratory variables

Laboratory parameters will be taken at baseline and summarized as part of baseline characteristics.

The summary statistics (including number, mean, median, Q1, Q3, standard deviation, minimum and maximum) of all laboratory variables) will be calculated by treatment group.

The incidence of PCSAs at any time during the treatment-emergent adverse event period will be summarized by biological function and treatment group whatever the baseline level and/or according to the following baseline status categories:

- Normal/missing
- Abnormal according to PCSA criterion or criteria

All measurements collected during the TEAE period, including values from unscheduled visits, will be considered for the PCSA summaries. These summaries will include patients in the safety population who have at least 1 assessment performed during the TEAE period. When a PCSA definition involves a change from baseline value, patients must also have a baseline value to be included in the summaries, and when required by the definition of the abnormality, patients must also have available laboratory normal ranges.

A listing of patients with at least 1 post-baseline PCSA during the on-treatment and post-treatment period (or out of normal range when no PCSA criterion is defined) will be provided which will display the entire patients' profile across time for all parameters belonging to the corresponding biological function. Individual data listings will include the following flags when applicable:

- Baseline values will be flagged "B".
- Normal laboratory ranges, available for most laboratory parameters, will be identified as ULN and LLN. Baseline, last on-treatment value, and individual data will be flagged "L" if the value is below the LLN and will be flagged "H" if it is above the ULN.
- Laboratory PCSA criteria will be used for the corresponding laboratory parameters. Values reaching a PCSA limit will be flagged (+, ++, -, or -- depending upon the direction and level of the abnormality). Flags for WBC and differential counts will be determined using data expressed in international units.

For parameters whose PCSA criteria are multiples of the ULN, the parameter's value will also be expressed as a multiple of the ULN in the individual data provided.

Drug-induced liver injury

The liver function tests, namely AST, ALT, alkaline phosphatase, and total bilirubin, are used to assess possible drug-induced liver toxicity. The proportion of patients with PCSA values at any postbaseline visit by baseline status will be displayed by treatment group for each parameter. The proportion of patients with PCSA values at any postbaseline visit will also be displayed by duration of exposure for each treatment group (only if a tabulation summary is necessary).

Listing of possible Hy's law cases identified by treatment group (e.g., patients with any elevated ALT > 3 x ULN, and associated with an increase in bilirubin ≥ 2 x ULN) with ALT, AST, alkaline phosphatase, total bilirubin, and the following complementary parameters (if available): conjugated bilirubin and prothrombin time/international normalized ratio, creatine phosphokinase, serum creatinine, complete blood count.

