2.4.5 Analyses of safety data

The summary of safety results will be presented by treatment group, for both the overall population and separately for each ethnic/race subgroup, for the 26-week randomized treatment period, unless specified otherwise.

All safety analyses will be performed on the safety population using the following common rules:

The “observation period” defined in [Section 2.1.4](#) is applicable in all safety analyses for the classification of AEs, determination of treatment-emergent Potentially Clinically Significant Abnormality (PCSA) values and the last on-treatment value for the laboratory, vital sign and ECG.

General common rules

All safety analyses will be performed on the safety population as defined in [Section 2.3.2](#), unless otherwise specified, using the following common rules:

- Safety data in patients who do not belong to the safety population (e.g., exposed but not randomized) will be listed separately
- The baseline value is defined as the last available value before the first dose of IMP
- PCSA values are defined as abnormal values considered medically important by the Sponsor according to predefined criteria/thresholds based on literature review and defined by the Sponsor for clinical laboratory tests, vital signs, and ECG. PCSA criteria will determine which patients had at least 1 PCSA during the treatment-emergent adverse event period, taking into account all evaluations performed during the treatment-emergent adverse event period, including nonscheduled or repeated evaluations. The number of all such patients will be the numerator for the treatment emergent PCSA percentage
- The treatment-emergent PCSA denominator by group for a given parameter will be based on the number of patients assessed for that given parameter in the treatment-emergent adverse event period by treatment group on the safety population.
- For laboratory parameters cited in the protocol as efficacy endpoints (including HbA1c and plasma glucose etc.), PCSA summaries will not be provided. These parameters will be summarized in [Section 2.4.4](#).

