- For quantitative safety parameters based on central laboratory/reading measurements, descriptive statistics will be used to summarize results and change from baseline values by visit and treatment group for the entire 26-week treatment period only. Summaries will include the last on-treatment value. The last on-treatment value is commonly defined as the value collected at the same day/time of the last administration of IMP. If this value is

missing, this last on-treatment value will be the closest value prior to the last dose administration of IMP during the entire 26-week treatment period.

- The analysis of the safety variables will be essentially descriptive and no systematic testing is planned. Relative risks versus Lantus and their 95% confidence intervals may be provided, if relevant

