Appendix C Study flow chart

STUDY FLOW CHART

Study Period	Screening		Open-label Randomized Treatment																	Follow-Up Visit	
	1	1.2 ^b	2	3	4	5	6	7	8	9	10	11	12	13	14	15	16	17	18	19 ^c	19 + 3
VISIT ^a				☎	☎	☎	☎	☎		☎	☎	☎	☎	☎		☎		☎	☎		☎
WEEK	-2	-1	0	1	2	3	4	5	6	7	8	9	10	11	12	15	18	21	24	26	26+3 days
Inclusion criteria including Informed Consent ^d	x		x																		
Exclusion criteria	x		x																		
Patient demography	x																				
Medical/surgical history (including diabetes)	x																				
Prior medication history	x	x																			
Physical examination	x																				
Height	x																				
Body weight and BMI ^e	x		x												x		x				x
Vital signs ^f	x		x						x						x		x				x
Diet and lifestyle counseling ^g	x		x						x						x		x				x
IRT contact ^h	x		x						x						x		x				x
Randomization			x																		
Dispensation of IMP (as appropriate)			x						x						x		x				
Pen-injector and self-injection training and re-training ⁱ			x	x	x	x	x	x	x	x	x	x	x	x	x	x	x	x	x		

Study Period	Screening		Open-label Randomized Treatment																	Follow-Up Visit	
	1	1.2 ^b	2	3	4	5	6	7	8	9	10	11	12	13	14	15	16	17	18	19 ^c	19 + 3
VISIT ^a				☎	☎	☎	☎	☎		☎	☎	☎	☎	☎		☎		☎	☎		☎
WEEK	-2	-1	0	1	2	3	4	5	6	7	8	9	10	11	12	15	18	21	24	26	26+3 days
Review and evaluation/adjustment of IMP doses			x	x	x	x	x	x	x	x	x	x	x	x	x	x	x	x	x	x	
Collection of used and unused IMP pens; compliance check									x						x		x			x	
Glucometer/supplies/diary dispensation			x																		
Glucometers, SMPG, hypoglycemia, insulin dose titration, diary training and re-training ⁱ			x	x	x	x	x	x	x	x	x	x	x	x	x	x	x	x	x		
SMPG ^j			x	x	x	x	x	x	x	x	x	x	x	x	x	x	x	x	x	x	
Two-hour standardized meal test (a sub-set of patients only)		x																		x	
HbA1c (central laboratory)	x														x		x			x	
FPG (central laboratory) (A 1-time repeat measurement before Visit 2 is permitted)	x														x					x	
PRO questionnaires ^k			x												x					x	
Hematology ^l	x																				
Serum chemistry ^m	x																				
Urinalysis ⁿ	x																				
eGFR ^o	x																				
Amylase, Lipase	x																				
Serum calcitonin			x																		
Pregnancy test ^p	x		x												x		x			x	
Concomitant medications	Continuously assessed and recorded throughout the study																				

Study Period	Screening		Open-label Randomized Treatment																	Follow-Up Visit	

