- g. Additional counseling will be performed as appropriate throughout the study.
- h. IRT will be contacted by the site at the pre-specified timepoints, as well as any other time when the patient needs re-dispensation of the IMP.
- i. Repeated as often as necessary, including during remote visits.
- j. SMPG monitoring is to be performed to guide insulin titration and for hypoglycemia evaluation, as appropriate, by study patients after Visit 2 and throughout the study duration
 - 1. Fasting (prebreakfast/preinjection) SMPG should be performed daily until the FPG target has been achieved. Thereafter, the number of fasting SMPG measurements could be reduced, according to the Investigator's judgment, however at least 3 fasting SMPG measurements per week must be done.
 Note: After randomization the fasting SMPG will follow the window for the preinjection SMPG
 - 2. Preinjection SMPG (within 30 minutes prior to the injection of Soliqua 100/33 or Lantus - if the latter is administered in the morning) during the randomized treatment period.
- k. PROs will be assessed per the following schedule:
 - 1. TRIM-D – to be done at Baseline, W12 and W26
 - 2. Patient/Physician assessments: W26.
- l. Hematology: erythrocytes, hemoglobin, hematocrit, leukocytes and platelets.
- m. Serum chemistry: AST, ALT, ALP, total bilirubin (if >ULN, then the direct and indirect sub-fractions must be measured), creatinine, uric acid, sodium, potassium
- n. Urinalysis: pH, glucose, ketones, leukocytes, blood/hemoglobin, protein.
- o. Using the Modification of Diet in Renal Disease (MDRD) equation.

p. Women of childbearing potential only; serum pregnancy test at Visit 1; urine pregnancy test at all subsequent visits for patients at traditional sites (if needed, a confirmatory serum pregnancy test can be performed). Investigators may conduct additional locally analyzed urine pregnancy tests as per their judgment. For patients participating at the designated site for the virtual study model, all pregnancy tests will be serum and for Visit 2, this may be done up to 1 week prior to the Visit 2 date (i.e., it may be done at Visit 1.2, if patient performs this visit; the results must be obtained prior to patient randomization).

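### Appendix C schedules the safety laboratory panels before treatment only, so the planned on-treatment laboratory changes and PCSA percentages would rest on unscheduled tests alone

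*SAP*

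**What the plan says.** Section 2.1.4.4 lists the safety laboratory data as hematology, clinical chemistry and urinalysis, and refers to Appendix C for the sampling visits. In Appendix C each of these three rows, including the one labelled "Serum chemistry ^m", has a single mark, at Visit 1 (Week -2). Footnote m places the liver tests in that panel: "Serum chemistry: AST, ALT, ALP, total bilirubin". Section 2.4.5.4 opens consistently with this: "Laboratory parameters will be taken at baseline and summarized as part of baseline characteristics".

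The analysis sections go further:

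- The common rules in section 2.4.5 state: "For quantitative safety parameters based on central laboratory/reading measurements, descriptive statistics will be used to summarize results and change from baseline values by visit". This covers the 26-week treatment period and includes a last on-treatment value. Section 2.5.3 repeats the by-visit display for the TEAE period.
- The same common rules fix the PCSA denominator: "The treatment-emergent PCSA denominator by group for a given parameter will be based on the number of patients assessed for that given parameter", within the TEAE period. Section 2.4.5.4 applies it to the laboratory data: "These summaries will include patients in the safety population who have at least 1 assessment performed during the TEAE period".
- For liver tests, section 2.4.5.4 adds: "The proportion of patients with PCSA values at any postbaseline visit by baseline status will be displayed by treatment group for each parameter".
- Section 2.4.5 leaves room for comparisons: "Relative risks versus Lantus and their 95% confidence intervals may be provided, if relevant".

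**The concern.** A PCSA percentage among assessed patients estimates incidence on treatment when nearly everyone is assessed on a fixed schedule. With no scheduled on-treatment test, the denominator becomes whoever happened to be tested. The trial is open-label, so the decision to test could depend on symptoms, on suspicion, or on the known treatment. A percentage from that group, set beside adverse event percentages that use the whole safety population, invites the reader to treat the two alike. A relative risk versus Lantus would compare two self-selected groups.

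The by-visit change tables have a related weakness. They could hold only unscheduled central laboratory values, because section 2.5.3 admits local results only to the PCSA summary, and only with a local normal range. At stake is the interpretability of the descriptive laboratory safety tables, and nothing beyond that.

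**Working it through.** No figure in the SAP needs reproducing here. The check sets the schedule beside the analyses and then illustrates the possible consequences.

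**Step 1: scheduled tests on treatment.** Reading the Appendix C rows column by column gives:

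| Row | Marked weeks |
|---|---|
| Hematology | -2 |
| Serum chemistry | -2 |
| Urinalysis | -2 |
| HbA1c (control) | -2, 12, 18, 26 |
| FPG (control) | -2, 12, 26 |

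The control rows keep their on-treatment marks in the same part of the table, so loss of marks in text extraction is an unlikely explanation. Some other rows look displaced by one column, but a lone Visit 1 mark moved one column would still lie in screening. Footnote c adds no test: the visit at rescue or permanent discontinuation repeats the Week 26 procedures, and Week 26 has no mark in these three rows.

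**Step 2: what can fill the planned tables.** HbA1c and plasma glucose, which are scheduled on treatment, are excluded from PCSA summaries by section 2.4.5. For the three panels the scheduled contribution to the TEAE period is therefore zero, and only unscheduled tests remain. Section 2.5.4 lets these into by-visit tables if they are re-allocated to a scheduled visit. Step 2 of section 2.5.3 re-allocates where a scheduled visit lacks a value, but does not say whether that covers a parameter with no scheduled post-baseline visit. If it does, Table 4 would label a value from any day between 1 and 83 as Week 6.

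**Step 3: illustration.** All inputs are assumed except the 120 patients per arm in section 1.3, and all 120 are taken as treated. Let N = 120, m = number tested, k = number of cases, p = true incidence.

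(a) All cases are among the tested, k = 3. The tested-only percentage is k/m; the safety-population percentage is k/N = 3/120 = 2.5%.

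(b) Testing is unrelated to abnormality, p = 2.5%. The expected tested-only percentage is p for any m. The chance of seeing no case is (1 - p)^m = 0.975^m. The expected safety-population percentage is p x m/N.

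| m | (a) k/m | (b) tested-only, expected | (b) chance of no case | (b) safety population, expected |
|---|---|---|---|---|
| 120 | 2.5% | 2.5% | 4.8% | 2.5% |
| 60 | 5.0% | 2.5% | 21.9% | 1.25% |
| 30 | 10.0% | 2.5% | 46.8% | 0.63% |
| 12 | 25.0% | 2.5% | 73.8% | 0.25% |

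**Step 4: unequal testing.** Under (a), with 3 cases in each arm and 30 versus 60 tested:

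- Tested-only: RR = (3/30)/(3/60) = 2.0; SE(log RR) = sqrt(1/3 - 1/30 + 1/3 - 1/60) = 0.785; 95% CI 0.43 to 9.32.
- Safety population: RR = (3/120)/(3/120) = 1.0; SE(log RR) = sqrt(1/3 - 1/120 + 1/3 - 1/120) = 0.806; 95% CI 0.21 to 4.86.

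The point estimate doubles through testing alone, although both intervals are wide and include 1. In (a) the safety-population figure is the right one; in (b) the tested-only figure is. Neither denominator serves in both cases, which is why both counts are needed.

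**The case against.** The strongest reply is that this is standard text carried over, with little effect in practice. Section 2.4.5.4 itself says that laboratory parameters are taken at baseline. By-visit statistics at scheduled visits give no post-baseline row if none is scheduled. Section 2.4 makes every analysis conditional on enough data, and the listings are planned anyway. The denominator is also openly stated as the number assessed, and scenario (b) shows that it can be unbiased. Much of this stands, and it keeps the point minor. It does not remove the point: section 2.4 gives no threshold and refers to early termination, not to absent scheduling, and nothing requires the tables to say that the tests were unscheduled or to show the safety-population N beside the percentage.

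Three stronger readings are tempting, and the SAP does not support them.

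- A reader might infer that the percentages are inflated. Why unscheduled tests are done is a matter for the protocol, which is not shown, so neither inflation nor its size can be asserted.
- A reader might infer that ALT elevations of special interest would be lost, because section 2.4.5.2 assigns them to the PCSA summary. An ALT event reported as an adverse event already enters the adverse event tables over the safety population, and the PCSA listing covers both the on-treatment and post-treatment periods.
- A reader might infer that Appendix C must be right and the analyses wrong. Appendix C may itself be the erroneous text.

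**Conclusion.** The inconsistency holds. The schedule and the opening sentence of section 2.4.5.4 point to pre-treatment sampling only, while sections 2.4.5, 2.4.5.4 and 2.5.3 plan on-treatment results from the same panels. If Appendix C is right, every laboratory PCSA percentage and by-visit change rests on patients with an unscheduled test and need not describe the safety population; any relative risk versus Lantus on that denominator shares the weakness. The direction and size are unknown, and the figures above only show what assumed inputs would produce. Severity is minor: the safety analysis is descriptive, no efficacy result is touched, and vital-sign PCSAs, which have scheduled on-treatment visits, are unaffected.

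**What to change.** Reconcile Appendix C with sections 2.4.5, 2.4.5.4 and 2.5.3. If safety laboratory tests were in fact scheduled on treatment, correct Appendix C; the planned summaries can then stay. If they were not, then for each parameter with no scheduled post-baseline test:

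1. Drop the by-visit change tables and state that unscheduled values are not re-allocated to visit windows.
2. Report PCSAs as listings and counts, always with both the number tested and the safety-population N. Label the tables as based on unscheduled tests.
3. Give no relative risk on the tested-only denominator.

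The cost is SAP wording, one extra column and fewer tables; no additional blood test is involved. The drawback is that a safety-population percentage counts untested patients as free of abnormality, so the table must call it a minimum figure.

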2.4.5.5 Analyses of vital sign variables

The summary statistics (including number, mean, median, Q1, Q3, standard deviation, minimum and maximum) of heart rate, temperature and respiratory rate (observed values, or mean of observed values, and changes from baseline) will be calculated for each visit or study assessment (baseline, each post-baseline time point, last on-treatment value) by treatment group.

The incidence of PCSAs at any time during the TEAE period will be summarized by treatment group for SBP, DBP and HR. All measurements collected during the TEAE period, including values from unscheduled visits, will be considered for the PCSA summaries. The summaries will include patients in the safety population who have at least 1 assessment performed during the TEAE period. When a PCSA definition involves a change from baseline value, patients must also have a baseline value to be included in the summaries.

A listing of patients with at least 1 post-baseline PCSA will be provided and will display the patient's profile over time of all vital sign parameters. Individual data listings will include the following flags:

- Baseline values will be flagged "B",
- Parameter values reaching a PCSA limit will be flagged (+, or - depending of the direction).

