2.1.3 Efficacy endpoints

All efficacy measurements collected during the study will be considered for analyses, including those obtained after IMP discontinuation or introduction of rescue therapy. Patients requiring rescue are identified as those with the reason for treatment ticked “rescue therapy” in e-CRF “Medication” page.

HbA1c, 2-hour PPG, FPG, glucose excursions are measured/calculated in a central laboratory (see study flowchart in [Appendix C](#)). Body weight, SBP and DBP are measured at on-site visits by the investigator or at the local testing center for subjects enrolled in the virtual sites. Efficacy variables will be summarized in both standard international units and conventional units when applicable.

Standardized meal test

A subset of randomized patients per treatment arm/race/ethnic group will undergo a standardized meal challenge to assess fasting and postprandial glucose (tested at a central laboratory), as well as the postprandial glycemic excursion, as part of the screening procedures and during Week 26.

In case of permanent discontinuation of treatment with IMP, the standardized meal test should be performed only if the patient receives treatment on the day of the visit. The meal test should also be performed at the end of study as planned.

If the patient drops out of the study, at the time of IMP discontinuation, regardless of whether the patient received IMP or not on the day of the meal test, the meal test should be performed.

Blood for plasma glucose is drawn 5 times:

- 30 minutes prior to the start of the meal (during Screening and at end-of-treatment for patients randomized to the Lantus PM dosing group) or before IMP administration (at Week 26 for the Soliqua 100/33 arm and for the Lantus AM dosing group);
- Just before the start of the standardized meal (Minute 0), at least 30 minutes after the Soliqua or Lantus AM dosing injection;
- 30 minutes after the start of the standardized meal;
- 60 minutes after the start of the standardized meal;
- 120 minutes after the start of the standardized meal.

Patients who are participating as part of the designated virtual study model will complete this meal test at a local laboratory testing facility.

Observation period

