2.1.4.5 Vital signs variables

Vital signs include: height, weight, BMI, heart rate (HR), systolic and diastolic blood pressure, (see study flowchart in [Appendix C](#) for designated visits). They will be performed after the patient has been seated for at least 5 minutes. Blood pressure and HR will be assessed 3 times with at least 1 minute between each measurement following the 5-minute rest period. The mean of the 3 measurements will be analyzed for each vital sign variable (HR, SBP, and DBP).

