If the severity/grade is missing for 1 of the treatment-emergent occurrences of an adverse event, the maximal severity on the remaining occurrences will be considered. If the severity is missing for all the occurrences, a “missing” category will be added in the summary table.

Handling of potentially clinically significant abnormalities

If a patient has a missing baseline he will be grouped in the category “normal/missing at baseline.”

For PCSAs with 2 conditions, one based on a change from baseline value or a normal range and the other on a threshold value, with the first condition being missing, the PCSA will be based only on the second condition.

For a PCSA defined on a threshold and/or a normal range, this PCSA will be derived using this threshold if the normal range is missing; e.g., for eosinophils the PCSA is > 0.5 GIGA/L or $>ULN$ if $ULN \geq 0.5$ GIGA/L. When ULN is missing, the value 0.5 should be used.

Measurements flagged as invalid by the laboratory will not be summarized or taken into account in the computation of PCSA values.

Linked adverse events that worsened or became serious

An AE that worsened or became serious will have a separate record in the data from the original event record with an AE identification number that links the new record to the original record. An AE that worsened or became serious will be considered a new recurring AE in the summary of recurrent events or in the summary of events by time intervals.

Handling of missing data for continuous efficacy endpoints

Please see [Section 2.4.4.1](#) and [Section 2.5.3](#).

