For the safety analyses, the baseline for a given parameter is defined as the last available measurement including unscheduled assessments, assessed prior to the first administration of IMP. For the efficacy analyses, the baseline for a given parameter is defined as the last available measurement including unscheduled assessments, assessed prior to the first administration of IMP or the last available value before randomization if not treated with IMP.

Summary statistics by visit for continuous efficacy endpoints

Summary statistics (number, mean, SD, SE, minimum, median, maximum) of continuous efficacy endpoints (observed data and change from baseline) will be provided at scheduled visits as per protocol. Summaries showing data by visit will be presented according to the visit number (or re-allocated visit number) and labeled with the targeted approximate day/week.

Last on-treatment value for laboratory variables and vital signs

The last on-treatment value is the final measurement assessed during the treatment epoch, regardless of the introduction of rescue therapy, including measurements at unscheduled visits.

Display of safety data by visit (laboratory variables and vital signs)

Descriptive statistics (number, mean, SD, minimum, median, maximum) of quantitative laboratory variables and vital signs (observed data and change from baseline) during the TEAE period will be provided at scheduled visits. In addition, these summaries will also include a row for the 'last value on-treatment' to describe the last available on-treatment value (see above). Summaries showing data by visit will be presented according to the visit number (or re-allocated visit number) and labeled with the targeted approximate day/week.

As specified in the study protocol, laboratory data from scheduled visits are reported by central laboratories. The local results will not be used in the efficacy analyses or in the definition of baseline for both safety and efficacy analyses. In the safety analyses, local results will only be used in the PCSA summary if they are accompanied by a local laboratory normal range.

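### Section 2.4.5.5 summarises two vital signs that the SAP lists nowhere else and leaves out blood pressure, and the SAP gives two opposing rules for change-based PCSAs when the baseline is missing

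*SAP*

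**What the plan says.** **Which vital signs.** Section 2.1.4.5 states: "Vital signs include: height, weight, BMI, heart rate (HR), systolic and diastolic blood pressure". It adds: "The mean of the 3 measurements will be analyzed for each vital sign variable (HR, SBP, and DBP"). Flow chart footnote f speaks only of blood pressure and heart rate. Section 2.4.5.5 nevertheless sets its summary statistics, per visit and for the last on-treatment value, on "heart rate, temperature and respiratory rate (observed values, or mean of observed values, and changes from baseline"). The next paragraph of 2.4.5.5 gives PCSA incidence for SBP, DBP and HR. Section 2.5.3 promises by-visit descriptive statistics, with change from baseline, for vital signs in general.

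**PCSA without a baseline.** Section 2.4.5.5 says: "When a PCSA definition involves a change from baseline value, patients must also have a baseline value to be included in the summaries". Section 2.4.5.4 has the same rule for laboratory data and also requires normal ranges where the definition needs them. Section 2.5.2 takes criteria that pair a threshold with either a change from baseline or a normal range, and says that "with the first condition being missing, the PCSA will be based only on the second condition".

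**Last on-treatment value.** In a bullet on central laboratory or central reading parameters, 2.4.5 says: "The last on-treatment value is commonly defined as the value collected at the same day/time of the last administration of IMP", with the closest earlier value as fall-back. Section 2.5.3, for laboratory variables and vital signs, says: "The last on-treatment value is the final measurement assessed during the treatment epoch". The opening of 2.4.5 ties the value to the observation period in 2.1.4.

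**The concern.** The section dedicated to vital signs is the one a programmer would follow for those tables. As written, it asks for two variables with no source in the SAP and does not ask for the two blood pressure variables that the SAP says it will analyse. A table shell built from 2.4.5.5 would differ from one built from 2.5.3.

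The two missing-baseline rules lead to different counts. The change condition in a vital-sign PCSA separates a new abnormality from one that was already there. If it is waived when the baseline is missing, a patient whose pressure was always high can enter the table as a treatment-emergent abnormality. If it is enforced, the same patient leaves both numerator and denominator. The choice should not be left open until the tables are programmed, least of all in an open-label trial.

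**Working it through.** No figure in the SAP needs reproducing. The check sets the texts side by side and works through what each rule does.

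**Step 1: variable list**

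| Place in SAP | HR | SBP | DBP | Temperature | Respiratory rate |
|---|---|---|---|---|---|
| 2.1.4.5, variables to be analysed | yes | yes | yes | no | no |
| Flow chart footnote f | yes | yes | yes | no | no |
| 2.4.5.5, summary statistics | yes | **no** | **no** | **yes** | **yes** |
| 2.4.5.5, PCSA incidence | yes | yes | yes | no | no |
| Appendix A, vital-sign criteria | yes | yes | yes | no | no |
| 2.5.3, by-visit display | vital signs in general, not itemised | | | | |

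The summary-statistics sentence is the odd one out. Two of its three variables have no source, and two of the three variables named for analysis are missing from it.

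**Step 2: criteria reached by the missing-baseline conflict** (Appendix A, rows read by unit and level)

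- HR: ≤50 bpm and a fall ≥20; ≥120 bpm and a rise ≥20
- SBP: ≤95 mmHg and a fall ≥20; ≥160 mmHg and a rise ≥20
- DBP: ≤45 mmHg and a fall ≥10; ≥110 mmHg and a rise ≥10

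That is 3 variables × 2 directions = 6 criteria, and every one pairs a threshold with a change. Among the laboratory criteria, change from baseline stands as a condition of its own (for example the haemoglobin decrease ≥20 g/L). ECG criteria also pair the two, but the flow chart has no ECG row. In this trial, then, the change-from-baseline part of the 2.5.2 rule bites on the vital signs, where 2.4.5.5 forbids it.

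**Step 3: one patient under each rule**

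Take an on-treatment SBP of 165 mmHg and no baseline.

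- 2.4.5.5: not included, so absent from numerator and denominator.
- 2.5.2: 165 ≥ 160, so counted as a treatment-emergent PCSA.
- With a known baseline, the criterion would need a baseline of at most 165 − 20 = 145. A patient who started at 150 has a rise of 15 and is not a PCSA. The 2.5.2 rule would count that patient if the 150 had gone unrecorded.

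The same happens with an HR of 48 bpm: 48 ≤ 50 is enough under 2.5.2, whereas the full criterion needs a baseline of at least 48 + 20 = 68.

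**Step 4: size per patient**

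Section 1.3 gives 120 patients per treatment. Assume all 120 are assessed and no other patient has the PCSA. One such patient moves the arm's percentage from 0/119 = 0% to 1/120 = 0.83%. Section 2.4.5 also asks for each ethnic/racial subgroup. The SAP gives no subgroup sizes; if the three were equal, 120/3 = 40 per arm, and the move is from 0/39 = 0% to 1/40 = 2.5%.

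**Step 5: how often**

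The flow chart marks vital signs at Visits 1 and 2, and 2.5.3 takes the last pre-dose value, unscheduled ones included. A treated patient lacks a baseline only if all of these are missing. The SAP gives no count; it should be small.

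**Step 6: last on-treatment value**

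For laboratory values, 2.4.5 stops at the last dose, while the period it invokes from 2.1.4 runs to 3 days after it. A measurement 2 days after the last dose is out under the first and in under the second. For vital signs, the texts that apply are that 2.1.4 period and the treatment epoch of 2.5.3, a term the SAP does not define. The TEAE period itself ends 3 days after the last injection in 2.1.4, but 10 days after it in 2.5.3 (1 day for hypoglycemia) for patients who stop treatment on or before Week 26.

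**The case against.** **Blood pressure is planned elsewhere.** Section 2.5.3 provides vital signs by visit with change from baseline, and 2.4.5.5 itself has SBP and DBP in the PCSA table. This stands. A reader might infer from 2.4.5.5 that no blood pressure changes would be produced; the SAP does not support that. What remains is that the dedicated section contradicts both 2.1.4.5 and the general rule. It does not help to say that blood pressure belongs to efficacy: 2.1.3 mentions how it is measured, but none of the endpoints in 2.1.3.1 to 2.1.3.3 is a blood pressure endpoint.

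**The two PCSA rules might be read together**, with 2.5.2 deriving the flag and 2.4.5.5 deciding who enters the table. That reading is possible, but the SAP does not state it. It would also leave patients flagged as PCSA in the listing and absent from the table.

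**Few patients are affected.** This stands, and it limits the weight of the point. Counting six criteria counts definitions, not patients.

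**An arm imbalance in the end-of-treatment row.** Because the meal-test text has samples "at end-of-treatment for patients randomized to the Lantus PM dosing group", a reader might infer that evening-dosed Lantus patients fall back from Week 26 to Week 18 while Soliqua patients do not. The documents do not support this. The same-day rule in 2.4.5 is confined to central laboratory or reading parameters, and blood pressure is measured by the investigator or at a local testing center (2.1.3). The flow chart marks hematology, chemistry and urinalysis at screening only, so no scheduled safety laboratory value exists to fall back from. The meal-test text does not fix when the last dose falls relative to the final vital signs.

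**Conclusion.** The point holds in two parts. First, the summary-statistics sentence in 2.4.5.5 has the wrong variable list: two entries have no source in the SAP, and SBP and DBP are missing. This rests on the SAP alone; the protocol is not at hand, so the claim is that the SAP does not list temperature or respiratory rate, not that no site records them. Second, 2.5.2 contradicts 2.4.5.4 and 2.4.5.5 on change-based PCSAs without a baseline. The conflict reaches all six HR, SBP and DBP criteria and moves a patient from excluded to counted, by about 0.8 percentage points per patient in an arm of 120. The number of such patients is probably small.

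The last on-treatment definitions are a minor consistency point only.

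The impact is confined to descriptive safety tables. Section 2.4.5 plans no systematic testing, and the primary endpoint is untouched. The correction is still worth making before programming, since it is cheap and changes what the tables show.

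**What to change.** 1. In 2.4.5.5, replace temperature and respiratory rate with SBP and DBP, so that the sentence matches 2.1.4.5 and 2.5.3.
2. In 2.5.2, remove the change-from-baseline case from the threshold-only rule, so that the exclusion in 2.4.5.4 and 2.4.5.5 governs. Align the normal-range case with 2.4.5.4, which requires normal ranges where the definition needs them, while 2.5.2 goes on without them.
3. As a minor point, state one last on-treatment definition for laboratory values and vital signs, tied to the on-treatment period in 2.1.4, and remove the competing sentences in 2.4.5 and 2.5.3. Reconcile the TEAE period length first (3 days in 2.1.4, 10 days in 2.5.3); otherwise the single definition inherits the ambiguity.

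The cost is SAP wording. No new data are needed. The few patients without a baseline leave the affected PCSA denominators; a footnote giving their number per arm would keep this visible.
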